## **9 Statistical design and analysis**

The variance known from the OLSA manual between normal hearing subjects aged 7-9 years is 3 dB, and 1.5 dB for adults over the age of 18.

A significance level of 0.05, a power of 0.8 and the approximate variance of 3 dB, a sample size of 24 is needed.

A non-parametric RM-ANOVA will be used for comparing the group OLSA results for the different conditions. Durbin-Conover pairwise comparisons will be used for post hoc analysis.

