## **4 Design of the clinical investigation**

This investigation is a single-group, single site, interventional study.

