## 6 Endpoints

The primary endpoint will be the difference in SRT- 50 levels using the adaptive Oldenburg Sentence Test (OLSA) between the following conditions:

1. Hearing aid Autosense Sky OS
2. Hearing aid Preferred setting (manual adjustments to the Noise Reduction and Directionality)
3. Hearing aid extreme setting with the Noise Reduction set to maximum and the Directionality set to minimum.

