## 8 Measurements and procedures

The investigation will have two lab visits and one home trial. The procedures are as follows:

Visit 1	Home Trial ~ 2 weeks	Visit 2

Audiogram, if needed
 
Obtain informed consent from parents
 
Fit study devices to match that of personal devices, verified with coupler measurements
 
Download myPhonak Jr app to personal or loaner smartphone and pair with
	
Participant instructed to use the app in five different situations and rate the ease of each situation, using the Assessment of hearing situations in children's every day lives".- To be completed after one week, and then after the second week.
	
Repeat dB SNR testing using OLSA (randomized order):
 
 
1. AutoSense Sky OS
 
2. Preferred Setting
 
3. Extreme setting
 
 
Interview and discussion of questionnaire results

study hearing aids
 
Train on app use
 
dB SNR obtained using the OLSA test with study devices in the following conditions: (randomized order):
 
 
1. AutoSense Sky OS
 
2. Preferred Setting
 
 
Extreme setting Give 2 copies of “Assessment of hearing situations in children’s every day lives” to complete during home trial
		
---	--	--

The test environment is set up as follows:

Cafeteria noise at 65 dBA, from four speakers (-50°, +50°, -130°, +130°)  
 Speech presented at 70 dBA, from front speaker (0°)

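### Section 9 does not say whether the Durbin-Conover pairs depend on a significant omnibus test and names no multiplicity adjustment; the one-visit false-positive chance is about 5% or about 12.6% accordingly, and a gate alone does not protect the null pair

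*Combined protocol and SAP*

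**What the plan says.** Section 6 defines the outcome as a comparison of three settings (AutoSense, preferred, extreme): "The primary endpoint will be the difference in SRT- 50 levels using the adaptive Oldenburg Sentence Test (OLSA) between the following conditions". Three settings give three pairs, and no pair is named as primary.

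Section 9 gives the analysis in two sentences. The first is the omnibus test: "A non-parametric RM-ANOVA will be used for comparing the group OLSA results for the different conditions". The second is "Durbin-Conover pairwise comparisons will be used for post hoc analysis". No sentence links the two by a decision rule, and no adjustment of the pairwise p-values is mentioned.

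The only error level in the plan is in the sample-size sentence: "A significance level of 0.05, a power of 0.8 and the approximate variance of 3 dB, a sample size of 24 is needed". The plan does not say whether that level applies to each pair, to the omnibus test or to the family, and it does not state sidedness.

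**The concern.** The objective in Section 2 is the effect on speech intelligibility of the changes children make in the app. The omnibus test cannot say which setting is better, so only a pairwise contrast, such as preferred against AutoSense, answers that question. The rule for declaring a pair different is therefore the rule for the trial's main claim, and it is not written down.

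The difficult case is a pair with p<0.05 under a non-significant omnibus test. Section 9 neither allows nor forbids reporting it as a finding on the primary endpoint, so the decision could be taken after the results are seen.

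A second weakness lies in the named test. The extreme setting may well differ clearly from the other two. If it does, the omnibus test will be significant and the gate will be open. The comparison of preferred with AutoSense then rests entirely on whether the pairwise test holds its own level.

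**Working it through.** **Inputs.** From Section 9: n = 24, level 0.05. From Section 6: k = 3 settings, hence 3 pairs. Degrees of freedom for Durbin-Conover: (24−1)(3−1) = 46, two-sided critical t = 2.013.

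Assumptions: the omnibus test is Friedman (chi-square, 2 df); scores are normal and independent around each child's own level; all 24 children are complete; one visit is analysed. A shift of 1 SD means one SD of a single score around the child's level. The plan does not give that SD unambiguously in dB.

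**Step 1: the plan's own figure.** The sample size of 24 cannot be derived from Section 9, because no target difference is given. If 3 is taken as the variance of a paired difference and 1 dB is assumed as the target, the normal formula gives (1.960 + 0.842)² × 3 / 1² = 23.5, so 24. An assumed 1.5 dB gives 11; reading 3 as an SD with 1 dB gives 71. The agreement at 24 depends on assumptions and does not settle how 0.05 is to be used across pairs.

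**Step 2: no true difference.** For a pair of settings i and j with rank sums Ri and Rj,

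t = |Ri − Rj| / √[2(nA − ΣRj²) / ((n−1)(k−1))],

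where A is the sum of squared ranks. Simulation under the global null (400,000 trials, untied scores) gives:

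| Rule | At least one significant pair |
|---|---|
| Pairs read regardless of the omnibus test, unadjusted | 12.6% |
| Pairs read only after a significant Friedman test | 5.3% |
| Holm over the three pairs, no gate | 4.4% |

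Some pair is significant under a non-significant omnibus test in 12.6 − 5.3 = 7.3% of null trials. As cross-checks on the 12.6%, the studentized range gives 12.0 to 12.2%, and three independent tests would give 1 − 0.95³ = 14.3%. With tied scores the ungated figure is 12.0%.

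**Step 3: one setting truly differs and the other two do not.** The denominator of t can be compared with the true spread of the rank-sum difference for the null pair. Without ties, A = 24 × (1 + 4 + 9) = 336 and nA = 8064.

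- No difference anywhere, rank sums 48, 48, 48: ΣRj² = 6912, so the standard error is √(2 × 1152 / 46) = 7.08. The true SD is √(24 × 2) = 6.93. The two agree.
- Third setting fully separated, rank sums about 36, 36, 72: ΣRj² = 7776, so the standard error is √(2 × 288 / 46) = 3.54. The true SD is √24 = 4.90. The standard error is too small.

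The error at full separation can be worked out exactly. The null pair's rank difference is d = 2X − 24 with X binomial (24, 0.5), and t = |d| / √[2(288 − d²/2)/46]. At |d| = 6, t = 1.75; at |d| = 8, t = 2.40. The pair is therefore declared different when X ≥ 16 or X ≤ 8, which has probability 2 × 1,271,626 / 16,777,216 = 15.2%.

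Error for the truly null pair, with the simulated values at intermediate shifts:

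| Shift of third setting | Gated Durbin-Conover | Holm Durbin-Conover |
|---|---|---|
| 1 SD | 6.6% | 5.1% |
| 2 SD | 10.9% | 10.9% |
| Full separation | about 15% | about 15% |

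At the larger shifts the gate is always open. Holm rejects the two real differences first and then tests the null pair at the full 0.05, so neither rule helps. Gated Wilcoxon signed-rank tests stay at or near 5% in the same settings.

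**Step 4: what the gate costs.** With one setting shifted 0.5 SD, any significant Durbin-Conover pair appears in about 46% of trials ungated and about 30% gated.

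**The case against.** The strongest reply is that post hoc tests placed after an omnibus test are ordinarily read only when the omnibus test is significant. On that reading the no-difference error is 5.3% and there is no inflation to report. This stands as far as it goes: a reader might infer that Section 9 tests the pairs without a gate, and the text does not say so. Nor does it state the opposite. The label gives an order of tests and no decision rule, so a report of an ungated pair would not depart from the plan.

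A reader might also say that 12.6% contradicts a promised 5%. The documents do not support that. The 0.05 is a sample-size input, and no family-wise rate is claimed anywhere.

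A third inference is that the error should be compounded over both visits, since Section 8 repeats the testing at Visit 2. Section 9 does not say that each visit is tested separately at 0.05, and any such figure needs an assumed between-visit correlation. It is left out here.

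Finally, this is a single-group study of marketed devices, and stating the usual sequence may look like mere clarification. That answers the gate. It does not answer Step 3, which applies even when the gate is taken as understood.

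**Conclusion.** The point holds as an unstated rule and a weak pairwise test. Section 9 contains neither a written gate nor an adjustment, and with 24 children, one visit and no true difference the chance of at least one pair with p<0.05 is about 5% or about 12.6% according to a sentence that is missing. Either simple repair fails where it matters: if the third setting truly differs, the null pair's gated Durbin-Conover error rises from about 6.6% at 1 SD to about 15% at full separation, and Holm does not correct the larger shifts.

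The 15% is an upper end for a setting ranked last, or first, in every child. The actual figure depends on how far apart the settings are, which the plan does not state. The simulated values assume normal, untied scores and complete data.

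**What to change.** Replace the post hoc sentence in Section 9 with wording to this effect: the three pairwise comparisons are made only if the Friedman test of the three conditions is significant at 0.05; a pair is declared different only if, in addition, the Wilcoxon signed-rank test on that pair's within-child differences is significant at two-sided 0.05; this family is tested once, and all other comparisons of the conditions are exploratory.

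With exactly three conditions, any two pairwise nulls together imply the global null. The rule is therefore a closed test and needs no further alpha split, provided each pairwise test holds its level. That proviso is why the pairwise test must change as well. The signed-rank test needs differences that are symmetric under the null, and another level-holding paired test would serve.

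The change takes a few lines of text, with no extra data or children. The price is that a pair with p<0.05 under a non-significant omnibus test can no longer be claimed. Step 4 shows that this loss is not negligible with 24 children, so it should be accepted knowingly.

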## **10 Investigation Duration**

The study is expected to last approximately 12 months to account for recruitment.

Each participant's expected study duration is approximately 4-6 weeks.

Each clinic appointment is expected to last between 1-2 hours.

## **11 Data handling and management**

Paper based CRFs will be used to capture the participant data. Both the objective data and the subjective data from the questionnaires will be manually transferred by the investigator to an electronic system, such as Microsoft Excel.

All CRFs are kept current to reflect the subject's status at each phase during the course of study. Participants cannot be identified in the CRF by name or initials and birth date but an appropriate coded identification is used. All study team members are authorized for the CRF entries and it is assured that any authorized person can be identified both for pCRFs and eCRFs. If pCRFs are used, the investigator's initials and subject ID are documented and data are entered into an electronic file for analysis by the respective investigator and data will be monitored by the assigned monitor. In case of a self-evident correction, either the subject does it by himself or the investigator undertakes the correction by crossing out the word/sentence with a single horizontal line and by adding the correction including his personal identifier and the date.

The pCRFs are only available to the local study team and to the monitor of the study. In the case of an audit or a serious adverse event, the CRFs may need to be de-anonymized and sent to the governing or notified body.

All paper-based data will be stored in a locked filing cabinet at the investigation site. All electronic data will be stored on an access-restricted computer owned by the investigation site. Permission to access data will be limited to study manager, monitor, PI, and essential research staff, as designated by the principal investigator.

During data collection of the investigation, physical copies of the data may be compiled and digitized by the investigator.

Data will be reviewed for mis-entries or inaccuracies as each data set is entered.

The extent and nature of monitoring appropriate for the clinical investigation including the strategy for source data verification (SDV) are based on considerations such as the objective, design, complexity, size critical data points and endpoints of the clinical investigation. A detailed plan for monitoring arrangements is provided separately from this CIP.

## **12 Amendments to the CIP**

Any necessary amendments to the CIP will be communicated to the study manager/sponsor. A new version of the CIP will be written, with the necessary changes and justification. The amended CIP will go through the necessary approval process.

## **13 Deviations from clinical investigation plan**

Deviations from the CIP to protect the rights, safety and well-being of human participants under emergency circumstances may proceed without prior approval of the sponsor and the EC – such deviations will be documented and reported to the sponsor representative (Study Manager) and the EC as soon as possible. Apart from that the investigator is not allowed to deviate from this CIP unless that deviation does not influence the investigation data.

## **14 Device accountability**

Sonova, in its capacity as sponsor, will maintain a log of all investigational devices, including the date of shipment from Sonova to the site, serial number, receiving study site, and date returned to Sonova.

The site will maintain a log of the devices provided by Sonova, including the date of receipt, serial number, date of fitting, participant identification, date of return to site by participant, and date returned to Sonova. Sonova will provide each site a template with which to record such information.

If a device needs to be replaced due to a device deficiency, the PI or sub-investigator will add the new device serial number, date of receipt, and date of return of the defective device on the Device Accountability Log.

In the case of a device deficiency, the Adverse Event-Device Deficiency form will be completed by the study manager and the PI or sub-investigators together.

## **15 Informed consent process**

Informed consent will be obtained from the legal guardians of the participants prior to any study participation in accordance with the ethics guidelines. The legal guardians will be granted sufficient time to read through the consent in full and ask any questions they have before signing. After the legal guardian signs the consent form, the researcher will sign and provide a copy to the legal guardian.

## **16 Adverse events, adverse device effects and device deficiencies**

Device deficiencies and all **adverse events (AE)** including all **serious adverse events (SAE)** are collected, fully investigated and documented in the source document and appropriate case report form (CRF) during the entire investigation period, i.e. from participant's informed consent until the last protocol-specific procedure, including a safety follow-up period (ISO-14155, 2020). Documentation includes dates of event, treatment, resolution, assessment of seriousness and causal relationship to device and/or investigation procedure.

Information on AEs is systematically collected during the regular investigation visits, and phone calls (if applicable).

The reporting of Serious Adverse Events and Device Deficiencies follows the Regulation (EU) 2017/745 and the MDCG 2020-10/1 Safety Reporting in Clinical Investigations of Medical Devices under Regulation (EU) 2017/745.

The causality assessment of the SAE will be conducted according to MDCG 2020-10/1 Safety Reporting in Clinical Investigations of Medical Devices under Regulation (EU) 2017/745.

## **17 Vulnerable populations**

This investigation includes children age 7 to 17.

## **18 Suspension or premature termination of the clinical investigation**

The study will be terminated if the majority of the participants are not able to wear the devices for the study visit.

The study will be terminated if the participants or researchers are exposed to safety risks other than those outlined in this document.

The study may be terminated in the event natural disasters, widespread outbreak of illness, compromised structure of the investigation site, etc. that would make continuation of the study impossible or impractical. The study will be suspended within 5 days of determination that the study or device put participants at an unreasonable risk.

If a participant is suspended, terminated, or withdraws from the study, their data can be traced with their unique study identification number.

Follow up of any SAEs will be conducted by the study manager and/or the PI until the nature of the event is resolved.

## **19 Publication policy**

The clinical investigation will be registered in clinicaltrials.gov, a publicly accessible database, as required by U.S. regulations.

An internal report of the results of this investigation will be completed and uploaded to eQMS. The PI may publish results at the completion of the investigation.
